Topical efinaconazole 10% solution (Jublia), which is a new FDA approved treatment for DLSO, has been shown to be efficacious and well tolerated by patients (Elewski, *et al*). In clinical trials, efinaconazole was applied daily to the nail plate, lateral and proximal nail folds, hyponychium and undersurface of the nail. Systemic absorption and associated toxicities are minimized with this topically applied medication. Complete cure and mycologic cure rates using efinaconazole 10% solution were within the range of those seen with oral antimycotic medications (Sporanox and Lamisil package inserts). Because efinaconazole 10% solution was applied in clinical trials directly onto clean, dry toenails that were free of toenail polish, it is not currently known if efficacy may be influenced by the wearing of toenail polish or if toenail polish is adversely modified by application of this medication. Toenail polish is very popular among women, especially during summer months, and wearing toenail polish is currently a major limitation of topical efinaconazole for treatment of DLSO. From our personal experience with efinaconazole solution, our patients have commented their nail polish becomes slightly tacky with daily application to the nail plate, but that application is still possible without discontinuing polish or treatment.

The dermatophytes causing DLSO primarily reside in the nail bed and subungual space, especially early in the disease process. Therefore we posit that application of efinaconazole solution to the nail bed and subungual space (subungual delivery) should be as efficacious as application to the nail plate. In fact, subungual delivery may prove to be more efficacious, as that space harbors the dermatophytes of DLSO.

Methods

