We will enroll 20 female subjects who fulfill the inclusion and exclusion criteria for a 52 week study (48 weeks treatment, 4 weeks post treatment follow-up). Ten women who self identify as frequently wearing toenail polish will be placed into the study group, while the control group will be comprised of 10 women who agree to abstain from wearing toenail polish during the length of the study. To avoid having a significant gender difference between both groups, male patients will be excluded since they would likely be exclusively placed into the control group. Because nail size is proportional to body size, with men having larger nails on average, excluding men will prevent introduction of bias in this study. Patients with symptomatic tinea pedis at screening will be treated with Luzu for 2 weeks.

Treatment methods will be similar to those described by Elewski, *et al.* Briefly, all patients will self-apply 1 drop of efinaconazole 10% solution to the hyponychium and undersurface of the nail every night before bed. Patients in the study group will not be restricted with respect to the brand of nail polish, however gel and plastic based polishes that are used in salons and that require curing will be prohibited. Patients in the study group will also be permitted to touch up their polish if needed in the morning without constraint.

Patients will be seen in clinic for this study at screening and then again at baseline. After baseline, patients will be clinically evaluated every month for the first 3 months, followed by 8-week intervals, with the final visit at week 52. Our primary outcome, compatibility of topical efinaconazole solution with wearing polish, will be assessed at every visit.

An interim analysis of our primary outcome will be performed at 3 months and these results will be presented in poster and oral format as well as submitted in manuscript form for publication in a peer reviewed journal. We hope to present these data as oral and poster presentations at the summer AAD, the Fall Clinical Dermatology Conference or other similar national meeting. We will also submit a manuscript regarding the compatibility of treatment with nail polish for publication in an appropriate dermatology journal for US audiences. At the conclusion of this study we will present our findings in poster and oral format, as well as submit a manuscript for publication in the Journal of The American Academy of Dermatology.

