Subjective effect of the medication on polish will be assessed with the following series of questions to which patients can answer yes or no:

- Were you able to apply the medication under your nail?
- Are you overall satisfied with Jublia?
- Is your polish tacky in the morning?

Patients will also answer the following question, which will be answered using a Likert or VAS scale where 0 represents no alteration in polish and 10 represents complete destruction of the polish:

- Is the quality of your polish diminished with use of Jublia?

We anticipate that some patients may note diminished quality of polish with use of Jublia on a daily bases, however we anticipate that this effect will be minimal.

Secondary outcomes will include efficacy and safety. Using 3rd party blinding, DLSO will be assessed at baseline and at every subsequent visit using the onychomycosis severity index, measuring percent of the target nail involved, and grading the infection from mild to moderate to severe. The target nail will be notched at baseline, thereby allowing overall nail growth to be assessed at each visit and disease free nail growth to be measured every 8 weeks. Photos of the nails will be taken every 8 weeks, including close up photos of the target nail with and without an outline of the onychomycosis. Fungal testing will be done at screening, 3 months, 7 months, end of treatment (48 weeks), and end of study (52 weeks). Clinical and mycologic cure will be evaluated at week 52. Mycology cultures will be processed at the fungal lab of the University of Texas, with whom the UAB Dermatology Research unit has a contract. The following will comprise our inclusion and exclusion criteria:

Inclusion:

- Female age 18-75,
- Clinical diagnosis of DLSO affecting at least 1 great toenail diagnosed with positive potassium hydroxide microscopy. A culture for a dermatophyte will be collected but positive culture is not necessary for inclusion in the study. Cultures for patients with a previous positive culture can be waived at the discretion of the investigator.
- Suitable for application of topical antifungal therapy, in the opinion of the investigator
- Target toenail thickness of 3mm or less as measured by digital caliper, as thickness greater than 3mm may allow inclusion of patients with severe onychomycosis, and this was the criteria used in the pivotal trial using topical efinaconazole for onychomycosis (Elewski BE, et al.)

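### Two of the four primary compatibility items suit only women still wearing polish and using the drug, and no item records stopping either because of its effect on the polish

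*Combined protocol and SAP*

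**What the plan says.** Methods names the primary outcome and its timing: "Our primary outcome, compatibility of topical efinaconazole solution with wearing polish, will be assessed at every visit". It is measured by four items put to the patient:

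- yes/no: "Were you able to apply the medication under your nail"
- yes/no: "Are you overall satisfied with Jublia"
- yes/no: "Is your polish tacky in the morning"
- 0-10: "Is the quality of your polish diminished with use of Jublia", where "0 represents no alteration in polish and 10 represents complete destruction of the polish"

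Only one group can supply polish ratings: "Ten women who self identify as frequently wearing toenail polish will be placed into the study group". The 10 controls agree to go without polish. Methods plans an interim analysis of the primary outcome at 3 months, for publication. The Research question section sets the final analysis at 52 weeks. Treatment lasts 48 weeks.

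The Background reports the investigators' earlier experience: polish became slightly tacky with daily use on the nail plate, but "application is still possible without discontinuing polish or treatment".

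The statistical statement at the end of the document names two-tailed t-tests for continuous variables and a 0.05 threshold. It gives no analysis set, denominator, missing-data rule or handling of women who stop polish or drug.

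**The concern.** A woman who gives up polish because the drug spoils it, or gives up the drug to save her polish, is a plain case of the two not working together. The plan has no place to record her. Once she has stopped, the tackiness and quality items no longer describe anything she is experiencing. She may leave them blank. If she has stopped polish, she may also answer literally that nothing is tacky, which would read as a good result.

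Whether a rating is missing or meaningless is then tied to the outcome itself. If such women fall out of the polish-specific summaries, what remains comes from those who tolerated the combination. That would push the result toward the protocol's own expectation of a minimal effect, in both the 3-month report and the final one. The reason for stopping is not collected, so the plan gives an analyst no means of repairing this afterwards.

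**Working it through.** **1. What each item can show once a woman has stopped**

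| Item | Stopped polish only | Stopped drug to save polish |
|---|---|---|
| Able to apply under nail | Answerable; may well be yes | Answerable; could be no, reason not given |
| Overall satisfied | Answerable; reason not given | Answerable; could be no, reason not given |
| Polish tacky | No valid answer | No valid answer about the drug |
| Polish quality, 0-10 | No valid answer | No valid answer about the drug |

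Two of the four items lose their meaning. The other two can register discontent but cannot attribute it to polish. A woman who stops only polish could answer yes to both and look like a success.

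**2. Size**

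The plan gives no figure to reproduce: it states no stopping rate, expected rating, margin or dropout. The one documented input is 10 polish wearers. The rest are assumptions: *k* women stop because of incompatibility, and those still rating average *m* on the 0-10 item.

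*Failure proportion.* Suppose no failure is seen among those still rating. Compare 0/(10 − k) with k/10, using exact (Clopper-Pearson) 95% intervals:

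| k | Stoppers left out | Stoppers counted |
|---|---|---|
| 1 | 0/9 = 0% (0 to 33.6%) | 1/10 = 10% (0.3 to 44.5%) |
| 2 | 0/8 = 0% (0 to 36.9%) | 2/10 = 20% (2.5 to 55.6%) |
| 3 | 0/7 = 0% (0 to 41.0%) | 3/10 = 30% (6.7 to 65.2%) |

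If 2 of 8 continuing women report tackiness, 2/8 = 25% becomes (2 + 2)/10 = 40% with two stoppers counted.

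*0-10 mean, with stoppers assigned 10.* Mean = ((10 − k) × m + 10 × k)/10. For m = 2 and k = 1: (9 × 2 + 10)/10 = 2.8.

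| m | k = 1 | k = 2 | k = 3 |
|---|---|---|---|
| 1 | 1.9 | 2.8 | 3.7 |
| 2 | 2.8 | 3.6 | 4.4 |
| 3 | 3.7 | 4.4 | 5.1 |

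*Chance of at least one stopper among 10*, 1 − (1 − p)^10, for an assumed stopping rate p: 40% at p = 5%, 65% at 10%, 89% at 20%, 97% at 30%.

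Stopping need not be common for at least one case to be likely, and one case moves the proportion by 10 points. The intervals are wide either way. What changes is the reported estimate and whether the failures are visible.

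**The case against.** Several stronger readings are tempting, and the documents do not support them.

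- **That the plan analyses only the ratings that happen to exist, and so drops stoppers.** It says nothing of the kind. Their handling is undefined, which is a gap and not a stated exclusion.
- **That a stopper has nothing to rate.** This is true of two items. The application and satisfaction questions remain open to any woman still attending. Visits are monthly for 3 months and then every 8 weeks, so she may also have rated her polish before stopping, and nothing says those ratings are discarded.
- **That the Background describes stopping as the problem.** It reports the reverse: patients could carry on. That experience was with the nail plate, whereas here the drug goes under the nail. Wearers may also choose their brand (apart from gel and plastic types that need curing) and touch up each morning. Stopping may be rare.
- **That each stopper should score 10 from then on.** The scale reserves 10 for complete destruction of the polish. A woman who stopped over slight tackiness did not report that, and she may resume. After week 48 nobody is on the drug.

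All four objections stand and limit the point. None removes it: no item records incompatibility-related stopping, and the two items that would show it best cannot be answered validly by the women concerned. Rarity is no reason to leave stopping unrecorded, since a documented count of zero would strengthen the compatibility claim.

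**Conclusion.** The point holds as a gap in measurement and in handling rules. A compatibility outcome should be able to register that a woman gave up polish or drug because of the effect on her polish, and this one cannot. The possible bias is toward compatibility and is confined to the polish-specific items. With 10 wearers, each unrecorded stopper is 10 percentage points of the group. The total is unknown, because every stopping rate and mean rating used above is assumed. A reader might infer that the primary result is biased. The documents support only that it could be, depending on how many women stop and how the analyst treats them. The change is worth making because it is cheap and the missing information would be hard to recover later.

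**What to change.** 1. At each on-treatment visit, ask whether since the last visit the woman has stopped polish or the medication because of its effect on her polish, and which of the two.
2. Report as a main compatibility result, at 3 months and at the end, the proportion of all 10 polish-group women with such stopping. Count it as a failure in the yes/no tackiness summary, with all 10 in the denominator.
3. Show the observed 0-10 ratings beside this, with the number rating. Assign 10 to stoppers only as a sensitivity analysis.
4. For women who leave for unknown reasons, give a best case (none counted as incompatible) and a worst case (all counted).
5. State these rules in the statistical section, including how a woman who resumes is treated.

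The cost is one question per visit and a short paragraph, and the compatibility figure may come out less favourable. Treatment is unaffected. If visits are already complete, the denominator of 10, the bounds and any reasons noted in the visit records can still be reported.

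### The primary polish outcome has no polish-without-drug reference, touch-ups are neither counted nor timed against the 0-10 score, and the SAP names no contrast for it

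*Combined protocol and SAP*

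**What the plan says.** The Background section names two unknowns: whether polish affects the drug's efficacy, "or if toenail polish is adversely modified by application of this medication". The second is the polish question. Methods makes it primary: "Our primary outcome, compatibility of topical efinaconazole solution with wearing polish, will be assessed at every visit".

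Four items measure it. Three are yes/no: ability to apply the drug, overall satisfaction, and morning tackiness. The fourth is scored from 0 (polish unaltered) to 10 (polish destroyed) and reads "Is the quality of your polish diminished with use of Jublia". The protocol expects some loss of quality but only a minimal effect.

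On exposure, Methods states that "all patients will self-apply 1 drop of efinaconazole 10% solution to the hyponychium and undersurface of the nail every night before bed" and that "the control group will be comprised of 10 women who agree to abstain from wearing toenail polish during the length of the study". On polish use it adds "Patients in the study group will not be restricted with respect to the brand of nail polish", apart from a ban on cured salon products, and "Patients in the study group will also be permitted to touch up their polish if needed in the morning without constraint". On visits before treatment: "Patients will be seen in clinic for this study at screening and then again at baseline".

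The statistical paragraph that closes the document has two sentences: two-tailed t-tests for continuous variables, and a 0.05 significance threshold. It names no outcome, contrast, visit or null value.

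**The concern.** The plan asks what the drug does to polish, but no group and no designated time point shows polish without the drug. Polish chips and dulls in ordinary wear. The quality item leaves each woman to subtract that herself, knowing that she is using Jublia. Morning repair then changes what is being scored, and the plan does not say whether the score refers to polish before or after repair, or over what period.

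This is the primary outcome. It is to be analysed at 3 months for presentations and a manuscript, and the protocol already anticipates a minimal effect. A low mean score could reflect a harmless drug, diligent touch-up, or generous netting-out of ordinary wear. A higher one could reflect ordinary wear alone. The data as planned could not tell these apart.

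**Working it through.** **Which polish and drug combinations are observed**

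| Group or time | Polish | Drug | Polish score usable as a reference? |
|---|---|---|---|
| Study group, on treatment (n = 10) | yes | yes | this is the quantity of interest |
| Control group (n = 10) | no | yes | no polish to score |
| Study group, screening and baseline | possibly | no | possible, but not designated; the item presumes use of Jublia |
| Study group, week 52 (4 weeks after treatment) | possibly | no | same |

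The yes/no tackiness item does not name the drug. Its problem is mainly the missing reference. The items on ability to apply and on satisfaction need neither a reference nor a touch-up record and are not affected.

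**Which t-tests could be applied to the 0-10 score**

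1. Between groups: not possible, because controls have no polish.
2. One-sample against 0: computable, but it counts as drug effect any ordinary wear that the patient does not net out.
3. Paired between visits: computable and the most useful, but not specified, and there is no suitable pre-drug item to pair with.

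**Illustration for option 2.** The plan does not state this test and the documents give no wear figure, so the inputs are assumptions. Take n = 10, two-sided 0.05, a true drug effect of zero, and residual wear of δ SDs of the score. The noncentrality is δ × √10, on 9 df.

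| δ | noncentrality | P(p < 0.05) |
|---|---|---|
| 0 | 0 | 5% |
| 0.25 | 0.79 | 11% |
| 0.5 | 1.58 | 29% |
| 1.0 | 3.16 | 80% |

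A paired change keeps the nominal 5% if ordinary wear is the same on both occasions.

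**Direction of bias.** Write reported score = (1 − r)(d + b), with d the drug effect, b the residual wear and r the share of damage hidden by repair. Then d = score/(1 − r) − b. For a reported mean of 2, with assumed b from 0 to 2 and r of 0 or 0.5:

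- r = 0: d = 2 − 0 = 2, down to 2 − 2 = 0.
- r = 0.5: d = 4 − 0 = 4, down to 4 − 2 = 2.

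Wear raises the score and repair lowers it, so the net direction is not known.

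**Precision after the fix.** The 95% CI half-width for a paired change, in SDs of the change, is t(0.975, n − 1)/√n. The change detectable with 80% power comes from the noncentral t.

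| pairs | t/√n | half-width | 80% power |
|---|---|---|---|
| 10 | 2.262/3.162 | 0.72 | 1.00 |
| 8 | 2.365/2.828 | 0.84 | 1.16 |
| 6 | 2.571/2.449 | 1.05 | 1.43 |

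Fewer than 10 pairs arise if some women wear no polish before the first dose. For the yes/no items, 0 of 10 reporting tackiness has an exact 95% upper limit of 1 − 0.025^(1/10) = 31%.

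The plan gives no SD, effect size, margin or power, so it has no figure of its own to reproduce.

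**The case against.** The outcome is openly subjective and is called compatibility. The study group are women who often wear polish, so they have experience to judge against, and the item asks for that judgement. Free touch-up and free choice of brand are part of normal use. This stands: impressions from 10 wearers in ordinary conditions are a legitimate, limited result, and touch-up and brand should stay unrestricted. But unmeasured, unblinded self-attribution is not a reference, and it does not answer the question posed in the Background.

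Compatibility is also to be assessed at every visit, which may include screening, baseline and week 52. This stands in part. Off-drug scores might be collected, but no within-patient comparison is named and the item's wording does not fit those visits.

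A reader might infer that the SAP rules out every valid test, or leaves only a test against 0. The text does not support that. It names no contrast, and a paired between-visit test is also a two-tailed t-test. It does not even say that the 0-10 score is among its continuous variables. Nor are the 11%, 29% and 80% rates the trial's error rates: they belong to an unstated test under assumed wear, and rejecting 0 would not itself produce a false claim of minimal effect.

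Finally, the fix leaves wide intervals and does not isolate the drug. That is true. It supplies a reference but does not make 10 women enough for a firm conclusion.

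**Conclusion.** The concern holds for the quality and tackiness items. With no polish-without-drug reference, no recall period, and no count or timing of touch-ups, the plan cannot separate drug effect from ordinary wear and repair. The SAP specifies no contrast for the 0-10 score and no method for the yes/no items. A statement that the effect on polish is minimal, or that it is not, would be unsupported; a description of patient impressions would be supported.

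The structural part rests on the text alone. The size does not: it depends on wear and repair, for which the documents give nothing. A reader might infer that touch-up biases the result towards a minimal effect, or that the drug probably harms polish. Neither follows, because wear and repair push in opposite directions. The point does not extend to the ability-to-apply and satisfaction items.

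This should be fixed, because it concerns the primary outcome and the remedy is cheap.

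**What to change.** 1. Keep the existing items and add drug-neutral versions of two: how altered the polish was (0-10), and whether it was tacky in the morning. Both should refer to polish before any touch-up, over one fixed recall period.
2. Ask them before the first dose in women then wearing polish, at each on-treatment visit, and at week 52. Two pre-drug visits already exist, so a woman without polish at screening can be asked at baseline.
3. At each visit record touch-ups and full re-applications since the last visit, and the polish brand. Restrict neither touch-up nor brand. Report these descriptively beside the score.
4. Make the polish analysis the paired within-patient change from pre-drug to week 12 (interim), and to one named on-treatment visit at or nearest the end of treatment, with 95% CIs. The visit must be named: 8-week intervals after month 3 do not obviously include week 48, when end-of-treatment fungal testing is listed. Use week 52 as a second, off-drug reference.
5. Report the yes/no items as polish-arm proportions with exact 95% CIs.
6. State that the reference is within-patient and unblinded, does not isolate the drug effect (brand is free and polish use is seasonal), and is imprecise. Describe any result without the reference as uncontrolled patient impression.

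Cost: two items, two counts, a brand field and a few SAP sentences, with no extra visits, staff or patients. The downsides are slightly more questionnaire burden, recall error in the counts, and possibly fewer than 10 pairs.

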Evaluating the Efficacy and Compatibility of Efinaconazole 10%
Solution (Jublia) for the Treatment of Toenail Onychomycosis in
Patients Wearing Toenail Polish Compared to Those without
Polish

Study Protocol & Statistical Analysis Plan

NCT03110029

January 14, 2019

[name]., Principal Investigator
University of Alabama at Birmingham
Birmingham, AL 35294

Evaluating the efficacy and compatibility of efinaconazole 10% solution (Jublia) for the treatment of toenail onychomycosis in patients wearing toenail polish compared to those without polish

Primary investigator: [name]

Research question

Topical efinaconazole 10% solution is known to be an efficacious and safe treatment modality for toenail onychomycosis. We propose to examine the compatibility of topical efinaconazole and nail polish in patients with distal and lateral subungual onychomycosis (DLSO). We posit that treatment of DLSO with efinaconazole 10% solution will not be adversely affected by the application of nail polish. We will have an interim compatibility analysis at 12 weeks and a final analysis at 52 weeks. We will also look at the efficacy of treating DLSO in patients wearing toe nail polish as compared to no polish when topical efinaconazole 10% (Jublia) solution is applied in the subungual space.

Background

DLSO is a commonly encountered dermatological disease. DLSO, which is caused by a variety of dermatophyte organisms, typically has an indolent and chronic course. Untreated, onychomycosis can pose a potential risk of spreading fungal infection to distant sites, which is especially true for elderly patients with comorbid diseases such as diabetes mellitus, peripheral vascular disease, or immunosuppression. Traditional therapies for DLSO have been comprised of mainly oral antifungal medications; however many of these treatments have side effect profiles that limit their applicability in this elderly population. Because of the potential toxicities associated with traditional oral therapies for DLSO, there has been great interest in finding safe and efficacious alternatives.

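### Does the promise of blinded nail scoring fail because the plan never says how polish is handled before the assessor looks?

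*Combined protocol and SAP*

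**What the plan says.** The Research question section states the expected result: "We posit that treatment of DLSO with efinaconazole 10% solution will not be adversely affected by the application of nail polish". Methods sets up two groups of 10 women. The study group describes itself as frequent polish wearers, while "the control group will be comprised of 10 women who agree to abstain from wearing toenail polish during the length of the study". Two rules govern polish in the study group: "gel and plastic based polishes that are used in salons and that require curing will be prohibited", and "Patients in the study group will also be permitted to touch up their polish if needed in the morning without constraint".

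On timing, "patients will be clinically evaluated every month for the first 3 months, followed by 8-week intervals, with the final visit at week 52". The compatibility outcome is collected on the same occasions: "Our primary outcome, compatibility of topical efinaconazole solution with wearing polish, will be assessed at every visit". It includes questions such as "Is your polish tacky in the morning".

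The secondary-outcome paragraph of Methods contains the only statement on masking: "Using 3rd party blinding, DLSO will be assessed at baseline and at every subsequent visit using the onychomycosis severity index". The same sentence adds the affected share of the target nail and a three-level severity grade. Nail growth from a baseline notch is read at each visit. Clear-nail growth and photographs, with and without the disease outlined, follow every 8 weeks. Clinical and mycologic cure are judged at week 52.

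Nothing in the protocol or the short statistical statement at its end describes polish removal, nail preparation, the identity of the third party, or how group is concealed.

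**The concern.** In most trials the assessor can be masked simply by not being told the group. Here the group marker may be painted on the organ being assessed. A study-group woman who keeps to the touch-up rule may arrive polished. That would tell the assessor her group and, if the polish is opaque, would also hide the nail plate. An assessor who hears the polish questions would learn the group by a second route.

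The protocol declares in advance that polish should do no harm, and the severity index, percent involvement and grade are visual judgements. Clear-nail growth and the visual part of clinical cure are exposed in the same way, although the masking sentence does not name them. The groups are self-selected, so masking is the only named protection against observer bias. If it failed, the comparison of polish with no polish could be tilted in either direction.

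**Working it through.** The plan states no figure on this point, so none can be reproduced. The check is to read the provisions together and count the readings involved.

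**1. What scoring requires.** The index, the affected share of the nail and growth from the notch are due at every scored visit. None can be read through opaque polish, so opaque polish has to come off at every scored visit, whether or not a photograph is due. Clear polish would not stop the measurement, but it would reveal the group, and the commitment to third-party masking rules that out. Both requirements lead to a bare nail in front of a masked scorer.

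**2. Whether another rule conflicts.** The touch-up permission concerns daily use. It does not say that polish stays on during scoring, and polish worn to the clinic can be removed there. The compatibility outcome consists of the patient's own answers, so it does not need the severity assessor to see the polish. No stated rule has to be broken for masking to work.

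**3. Readings involved.** Take a month as 4 weeks (an assumption; it fits the 7-month fungal test, since 7 × 4 = 28 falls on the visit grid).
- Visits after baseline: weeks 4, 8, 12, then 20, 28, 36, 44, 52, which makes 8.
- Study-group readings with no dropout: 10 × 8 = 80.
- Week 48 is named as end of treatment and a fungal-test time. If it is also a scored visit: 10 × 9 = 90.

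**4. What the photographs add.** Outlined photographs of the diseased area also imply a bare nail, so one can ask which of the 8 visits they reach.
- Counted from week 4 (4, 12, 20, 28, 36, 44, 52): 7 of 8 visits, leaving 1 × 10 = 10 readings without one.
- Counted from week 12 (12, 20, 28, 36, 44, 52): 6 of 8 visits, leaving 2 × 10 = 20.
- Counted from baseline (0, 8, 16, 24, 32, 40, 48): only week 8 matches, leaving 7 × 10 = 70. This would need photographs at weeks 16, 24, 32 and 40, when no visit is scheduled, so it is not a credible reading.

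The defensible range is 10 to 20 of 80 readings without a photograph. That figure measures neither polish on the nail nor bias, because step 1 already implies a bare nail at every scored visit. The count does show that reading the planned photographs alone could not supply masked scores at every visit, so at least some scoring must be done live.

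**5. Outcomes outside the gap.** The compatibility answers come from the patient. Cultures go to an outside laboratory and are less exposed, although masking of that laboratory is not stated.

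**The case for a change.** The strongest reply is that an intention to remove polish is not a procedure. Removal in front of the assessor reveals the group as surely as leaving the polish on. Removal in one group only can leave stain, residue or solvent traces that mark that group. The polish questions are asked at the same visits, and no one is told to keep the answers from the assessor. Efficacy stands in the title and in the research question, and a written visit order would cost little.

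All of that is accurate as a description of what the text leaves open. It shows that masking could be handled badly; it does not show that the plan directs anyone to handle it badly. The protocol commits to a masked third party at every visit. The obvious way to honour that is for other staff to ask the questions and prepare all nails alike in both groups before the assessor enters. Writing this down would record how to do what is already promised, without altering an outcome, a comparison or an analysis. The statistical statement is also in the past tense, so the visits may be over.

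What stands is a reporting point. The study report should say how masking was kept. If it was not kept, the visual outcomes should be described as not reliably blinded.

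**Conclusion.** No change to the plan. The omission is real, but it is missing operational detail that competent staff would fill sensibly. The commitment to masked scoring and the need for a visible nail already point to the right conduct, and no stated rule leads to a wrong result.

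The gap covers at most 80 study-group readings after baseline, or 90 with week 48, all on secondary visual outcomes. The counts assume four-week months and no dropout. That polish is worn on the target nail is inferred, not stated. Any bias is of unknown size and direction. Even perfect masking would leave the confounding that comes from comparing 10 with 10 self-selected women.
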